**Table 4 Schedule of Activities for Part B, Cohort 3**

Procedures	Screening Period		Treatment Period														Follow-up	ET s			
	Day -30 to -2	Day -1	Day 1	Day 2	Day 3	Day 4	Day 5			Day 6			Day 7			Day 8	Day 14				
		Hour a	1	25	37	49	61	73	85	97	100	103	109	121	124	127	133	145	148	151	169
Informed consent	X																				
Urine drug/cotinine/alcohol test	X		X t																		
Virology test s	X																				
Demographics b	X		X																		
Medical and surgical history	X																				
Check In			X																		
Serum pregnancy test c			X																		
Apixaban d				X	X	X	X	X	X				X	X			X	X			
LT3001 drug product				X t						X	X	X		X	X	X		X	X	X	
Physical examination e	X			X					X									X		X	X
Vital sign f	X		X	X	X	X		X		X	X	X		X	X	X		X	X	X	
12-lead ECG assessment g	X		X	X	X	X		X		X				X				X		X	X
LT3001PK blood sample																					
Apixaban PK blood sample j																					
Platelet function test			X k						X k	X l								X m		X	X
Coagulation n	X		X t						X k	X l								X m		X	X
Hematology test o	X		X t						X									X		X	X
Clinical chemistry test p	X		X t						X									X		X	X
Urinalysis q	X		X t						X									X		X	X
Discharge																		X			

Prior and concomitant medication	X	X	X
Adverse event	X	X	X

ECG = electrocardiogram; ET = early termination; PK = pharmacokinetic

- a. Virology tests will include HIV antibody, HBsAg, hepatitis C virus antibody, and COVID-19 antibody.
- b. Demographics will include age, gender, height, body weight, BMI and race. On Day -1, only body weight will be measured.
- c. Serum pregnancy test will be performed in female subjects of childbearing potential within 24 hours prior to the first drug treatment on Day 1.
- d. The first dose of apixaban on Day 5, Day 6 and Day 7 will be followed immediately by [REDACTED] LT3001 administered as a 15-minute IV infusion
- e. Physical examination will be performed at screening visit, pre-dose on Day 1, the end of apixaban single treatment on Day 4, the end of combination treatment on Day 7 and follow-up visit on Day 14.
- f. Vital signs will include body temperature, blood pressure, respiratory rate, and heart rate. Measurements will be made after the subject has rested in a supine position for at least 3 minutes. Blood pressure will be assessed in seated and supine position at predose and 60 minutes after dosing/infusion, only supine position at 20 minutes after dosing/infusion. Vital signs will be assessed at screening visit, Day 1 to 4 (pre-dose), Day 5 to Day 7 (each LT3001 dosing period at pre-dose, 20 minutes and 60 minutes after infusion is initiated) and follow-up visit on Day 14.
- g. A 12-lead ECG assessment will be [REDACTED].
- h. PK blood samples of LT3001 will be collected [REDACTED].
- i. PK blood samples of LT3001 will be collected [REDACTED].
- j. PK blood samples of apixaban will be [REDACTED].
- k. Platelet function test and coagulation test will be [REDACTED].
- l. Platelet function test and coagulation test will be measured on the first dose of LT3001 at 15 min after infusion is initiated (end of infusion) on Day 5
- m. Platelet function test and coagulation test will be measured on the last dose of LT3001 at 15 min after infusion is initiated (end of infusion) on Day 7
- n. Coagulation parameters will include PT, INR, aPTT and TT.
- o. Hematology tests will include Hb, RBC, MCV, Hct, MCH, WBC, WBC-DC, and platelets.
- p. Clinical chemistry tests will include BUN, creatinine, fasting blood glucose, ALP, ALT, AST, GGT, total bilirubin, total proteins, albumin/globulin ratio, Na, K, Cl, Ca, bicarbonate, uric acid, CK, cholesterol, triglycerides, free iron, and ferritin.
- q. Urinalysis will include dipstick urinalysis and microscopic examination.
- r. When the urine drug/cotinine/alcohol tests and/or clinical laboratory tests including coagulation, hematology and clinical chemistry are performed on Day -4 to Day -2, these tests need not be repeated on Day -1.
- s. In the event of early termination (ET), a randomized subject will complete the ET procedures. The collection of PK blood samples of LT3001 and/or apixaban can be

exempted based on the Investigator's discretion if the subject did not receive the indicated study drug.

- t. A single dose of LT3001 drug product will be given on Day 1
- u. A 30-minutes window is allowed for non-PK procedures.

Table 5 Schedule of Activities for Part B, Cohort 4

Procedures	Screening Period		Treatment Period															Follow-up	ET s	
	Day -30 to -2	Day -1 Hour u	Day 1	Day 2	Day 3	Day 4	Day 5					Day 6				Day 7			Day 8	
			1	25	37	49	61	73	85	97	100	103	109	121	124	127	133	145	148	151
Informed consent	X																			
Urine drug/cotinine/alcohol test	X	X r																		
Virology test a	X																			
Demographics b	X	X																		
Medical and surgical history	X																			
Check In		X																		
Serum pregnancy test c		X																		
Dabigatran d			X	X	X	X	X	X	X			X	X			X	X			
LT3001 drug product				X t						X	X	X		X	X	X		X	X	X
Physical examination e	X		X				X											X		X
Vital sign f	X	X	X	X	X	X		X	X	X		X	X	X		X	X	X		X
12-lead ECG assessment g	X	X	X	X	X	X		X			X				X				X	X
LT3001 PK blood sample																				
Dabigatran PK blood sample j																				
Platelet function test																				
Coagulation h	X	X r								X k	X l							X		X
Hematology test o	X	X r								X								X		X
Clinical chemistry test p	X	X r								X								X		X
Urinalysis q	X	X r								X								X		X
Discharge																		X		
Prior and concomitant medication	X	X																		
Adverse event																				

ECG = electrocardiogram; ET = early termination; PK = pharmacokinetic

- a Virology tests will include HIV antibody, HBsAg, hepatitis C virus antibody, and COVID-19 antibody.
- b Demographics will include age, gender, height, body weight, BMI and race. On Day -1, only body weight will be measured.
- c Serum pregnancy test will be performed in female subjects of childbearing potential within 24 hours prior to the first drug treatment on Day 1.
- d The first dose of dabigatran on Day 5, Day 6 and Day 7 will be followed immediately by [REDACTED] LT3001 administered as a 15-minute IV infusion
- e Physical examination will be performed at screening visit, pre-dose on Day 1, the end of dabigatran single treatment on Day 4, the end of combination treatment on Day 7 and follow-up visit on Day 14.
- f Vital signs will include body temperature, blood pressure, respiratory rate, and heart rate. Measurements will be made after the subject has rested in a supine position for at least 3 minutes. Blood pressure will be assessed in seated and supine position at predose and 60 minutes after dosing/infusion, only supine position at 20 minutes after dosing/infusion. Vital signs will be assessed at screening visit, Day 1 to 4 (pre-dose), Day 5 to Day 7 (each LT3001 dosing period at pre-dose, 20 minutes and 60 minutes after infusion is initiated) and follow-up visit on Day 14.
- g A 12-lead ECG assessment will be performed at screening visit [REDACTED]
- h PK blood samples of LT3001 will be [REDACTED]
- i PK blood samples of LT3001 will be [REDACTED]
- j PK blood samples of dabigatran will be collected [REDACTED]
- k Platelet function test and coagulation test will be [REDACTED]
- l Platelet function test and coagulation test will be measured on the first dose of LT3001 at 15 min after infusion is initiated (end of infusion) on Day 5
- m Platelet function test and coagulation test will be measured on the last dose of LT3001 at 15 min after infusion is initiated (end of infusion) on Day 7
- n Coagulation parameters will include PT, INR, aPTT and TT.
- o Hematology tests will include Hb, RBC, MCV, Hct, MCH, WBC, WBC-DC, and platelets.
- p Clinical chemistry tests will include BUN, creatinine, fasting blood glucose, ALP, ALT, AST, GGT, total bilirubin, total proteins, albumin/globulin ratio, Na, K, Cl, Ca, bicarbonate, uric acid, CK, cholesterol, triglycerides, free iron, and ferritin.
- q Urinalysis will include dipstick urinalysis and microscopic examination.
- r When the urine drug/cotinine/alcohol tests and/or clinical laboratory tests including coagulation, hematology and clinical chemistry are performed on Day -4 to Day -2, these tests need not be repeated on Day -1.
- s In the event of early termination (ET), a randomized subject will complete the ET procedures. The collection of PK blood samples of LT3001 and/or dabigatran can be exempted based on the Investigator's discretion if the subject did not receive the indicated study drug.
- t A single dose of LT3001 drug product will be given on Day 1.
- u A 30-minute window is allowed for non-PK procedures.

### 3. Introduction

### 3.1. Study Rationale

This Phase 1 study (LT3001-105) is planned to establish the clinical safety and pharmacokinetics (PK) profile of multiple dose of LT3001 drug product [REDACTED] and to investigate drug interactions of LT3001 with potential concomitant medications in healthy subjects.

### 3.2. Background

A grid of 20 horizontal black bars of varying lengths. The bars are arranged in a single row. The lengths of the bars are as follows: 1, 1. The bars are evenly spaced and extend across the width of the grid.

LT3001 is a novel small molecule with both cerebral blood flow restoration and free radical-scavenging activities as shown in nonclinical studies and thus can potentially be a new therapy for treating acute ischemic stroke.

A Phase 1 single IV infusion of LT3001 drug product in health volunteer study (LT3001-101) has been completed at a clinical site in the United States, which indicate that the LT3001 drug product is safe and well tolerated at all doses tested (single dose of [REDACTED] given as a 15 minute IV infusion).

The safety of LT3001 with concomitant drugs commonly used by acute ischemic stroke patients is therefore of great interest. Antiplatelet agents, such as aspirin and clopidogrel, are used for both the management of acute ischemic stroke and the prevention of stroke. Anticoagulants including apixaban and dabigatran are commonly used for stroke prevention in atrial fibrillation patients.

### 3.2.1. Nonclinical Studies

LT3001 is a novel small molecule designed to have both thrombolytic and free radical-scavenging activities, which were characterized in various in vitro and in vivo models. In vitro studies have shown that LT3001 exhibited substantial antioxidation activity. In animal studies LT3001 can restore blood flow, reduce cerebral infarct volume, and improve neurological outcome in rodent and nonhuman primate stroke models, with an apparent wider therapeutic time window and a better safety profile than those reported for rtPA. The effect of LT3001 on the bleeding time was evaluated in male ICR mice and was comparable to animals that received vehicle control and significantly shorter than those treated with rtPA (10 mg/kg).

A series of horizontal black bars of varying lengths, likely a redacted list of names or a visual representation of data.

The entire page content is obscured by a large, solid black rectangular redaction box, indicating that the original text has been completely removed or is not to be disclosed.

### 3.2.2. Clinical Studies

A series of horizontal black bars of varying lengths, likely a redacted text block. The bars are arranged vertically, with some being full lines and others being shorter segments, suggesting a line of text that has been obscured.

### 3.2.3. Safety

Clinical evidence in healthy subjects indicate that the LT3001 drug product is safe and well-tolerated at the doses tested (ie, single doses of [REDACTED] given as a 15-minute IV infusion).

### 3.3. Benefit/Risk Assessment

The dose selected for this multiple-dose study had been previously evaluated in a single dose study. There were no clinically significant changes in safety parameters. No clinical efficacy studies have been completed with LT3001 Drug Product, so a direct benefit-risk assessment has not been performed.

More detailed information about the known and expected benefits and risks and reasonably expected adverse events of LT3001 may be found in the Investigator's Brochure.

[figure not shown]
#### 4. Objectives and Endpoints

Objectives	Endpoints
Primary	
Part A 

To determine the safety, tolerability, and PK of a 3-day TID use of LT3001 drug product, when administered as an IV infusion q3h between each dose within one day in healthy subjects (with half Chinese population).

	Part A 

Nature and severity of adverse events (AEs) and number of subjects with AEs

Changes from baseline in physical examination, vital signs, electrocardiogram (ECG) assessment, oximetry, coagulation, and clinical laboratory tests.

Plasma PK parameters of LT3001

Urine PK parameters of LT3001

Effects of LT3001 drug product on systolic and diastolic blood pressure (SBP/DBP), prothrombin time (PT), activated partial thromboplastin time (aPTT), and thrombin time (TT)

Part B 

To determine the safety and PK of LT3001 when coadministered with aspirin, clopidogrel, apixaban or dabigatran

	Part B 

Nature and severity of AEs and number of subjects with AEs

Changes from baseline in physical examination, vital signs, ECG assessment, oximetry, platelet function test, coagulation, and clinical laboratory tests.

Plasma PK parameters of LT3001

Plasma PK parameters of aspirin, clopidogrel, apixaban and dabigatran

## 5. Study Design

### 5.1. Overall Design

This study is a two-part study (Figure 1). Part A is double-blind, placebo-controlled, and will examine the safety and PK profiles of multiple doses of LT3001 drug product in healthy subjects. Part B is open-label and will assess the safety and PK of LT3001 when coadministered with aspirin, clopidogrel, apixaban or dabigatran.

After provision of written informed consent, each subject will be evaluated for study eligibility during the screening period, which is within 30 days prior to receiving the study drug (Day 1).

#### Part A

Eligible subjects will be admitted to the site on Day -1 and undergo additional eligibility assessments. Those reconfirmed as eligible will be randomly assigned to study treatment. Approximately 16 healthy subjects will be randomized in a 3:1 ratio to receive either LT3001 drug product [REDACTED] or placebo administered as a 15-minute intravenous (IV) infusion. Each subject will receive three doses, administered 3 hours apart, on Days 1, 2, and 3. Subjects will be released from the site on Day 4 following all safety and PK procedures.

The first 4 subjects will be “sentinel subjects,” with 2 subjects assigned to receive LT3001 drug product and the other 2 subjects assigned to receive placebo. The Investigator will review all available safety data from the sentinel subjects. If considered safe to do so, the remaining subjects will be dosed.

The remaining subjects may not proceed to receive study drugs in the event of any of the following:

- A subject treated with LT3001 drug product experiences any hemorrhage which is assessed as related to LT3001 drug product
- A subject treated with LT3001 drug product experiences any SAE is assessed as related to LT3001 drug product (at least possibly related)
- Safety concerns per the Investigator's clinical judgment

The dosing schema is summarized below.

The safety observation period may be extended beyond Day 4 in the event of any signal of significant clinical concern raised by the Investigator.

It will require approximately 5 weeks for each subject to complete all the required study procedures of Part A, including screening period, and blood samples will be collected from each subject for safety and PK evaluation during the study. Duration of both inpatient stay and PK sampling may be subject to change, depending on emerging safety and PK results.

After all healthy subjects complete study procedures of Part A, the safety review meeting will be held by the Investigator and the sponsor medical monitor (or designee) to review all available safety and blood PK data of all subjects and determine whether one or more of the following should occur:

- Enrollment of subjects of Part B will proceed
- More subjects should be enrolled, up to a maximum of 16 subjects in LT3001 drug product group, based on safety and blood PK data
- Refinement of PK sampling times is recommended
- A protocol amendment is recommended

#### Safety Review Schema

## Part B

Part B is open-label without placebo control. Approximately 48 subjects will be sequentially enrolled into four cohorts with 12 subjects in each cohort.

The first **3** subjects of each cohort will be “sentinel subjects”. After each sentinel subject completes the first day of combination treatments, the Investigator will review all available safety data from the sentinel subjects. If considered safe to do so, each sentinel subject will receive the remaining combination treatments.

The remaining combination treatments in a sentinel subject may not proceed in the event of any of the following:

- A subject experiences any severe hemorrhage which is assessed as related to the combination treatment
- A subject treated with LT3001 drug product experiences any SAE related to study drug (at least possibly related)
- Safety concerns per the Investigator’s clinical judgment

The dosing schema is summarized below.

Each Cohort of Part B	Sentinel Subjects	Remaining Subjects
Number of Subjects	3	9

In **Cohort 1**, each subject will receive a single 15-minute infusion of LT3001 [REDACTED] on Day 1. Each subject will receive multiple-dose aspirin as follows: a loading dose of 325 mg aspirin on the morning of Day 2 followed by a daily maintenance dose of 81 mg aspirin on Days 3 through 8 (Figure 2). The regimen is intended to achieve its maximal inhibitory effects on platelet function. Aspirin will be administered after breakfast. On the morning of Day 6, the dose of aspirin will be followed by the first dose of LT3001 0.025 mg/kg administered as a 15-minute IV infusion. Subjects will receive 9 doses of LT3001 on Days 6 through 8 (TID q3h). Each subject will be admitted into the study site on Day -1, stay until Day 8, and will have a follow-up visit on Day 15.

**Figure 2 Dosing Schema of LT3001 and Aspirin Co-administration**

In **Cohort 2**, each subject will receive a single 15-minute infusion of LT3001 [REDACTED] on Day 1.

Each subject will receive multiple-dose clopidogrel as follows: a loading dose of 300 mg clopidogrel on Day 2 followed by a daily maintenance dose of 75 mg clopidogrel on Days 3 through 9, a dosing paradigm consistent with clinical use in relevant indications (Figure 3). Clopidogrel will be administered after breakfast. On Day 7, the dose of clopidogrel will be followed by the first dose of LT3001 [REDACTED] administered as a 15-minute IV infusion. Subjects will receive 9 doses of LT3001 on Days 7 through 9 (TID q3h). Each subject will be admitted into the study site on Day -1, stay until Day 10, and will have a follow-up visit on Day 16.

**Figure 3 Dosing Schema of LT3001 and Clopidogrel Co-administration**

In **Cohort 3**, each subject will receive a single 15-minute infusion of LT3001 [REDACTED] Day 1. Each subject will receive multiple-dose apixaban as follows: 5 mg apixaban twice daily (BID) every 12 hours (q12h) on Days 2 through 7 (Figure 4). The morning doses of apixaban will be administered after breakfast. Given that the half-life of apixaban is 9 to 14 hours, the 3-day apixaban BID treatment allows for reaching over 5 half-lives and 97% steady state of apixaban before the coadministration of apixaban and LT3001. On Day 5, the first dose of apixaban will be followed by the first dose of LT3001 0.025 mg/kg administered as a 15-minute IV infusion. Subjects will receive 9 doses of LT3001 on Days 5 to 7 (TID q3h). Each subject will be admitted into the study site on Day -1, stay until Day 8, and will have a follow-up visit on Day 14.

**Figure 4 Dosing Schema of LT3001 and Apixaban Co-administration**

In **Cohort 4**, each subject will receive a single 15-minute infusion of LT3001 [REDACTED] Day 1. Each subject will receive multiple-dose dabigatran as follows: 110 mg dabigatran BID (q12h) on Days 2 through 7 (Figure 5). The morning doses of dabigatran will be administered after breakfast. Given that the half-life of dabigatran is 12 to 17 hours, the 3-day dabigatran BID treatment allows for reaching over 4 half-lives and 94% steady state of dabigatran before the coadministration of apixaban and LT3001. On Day 5, the first dose of dabigatran will be followed by the first dose of LT3001 0.025 mg/kg administered as a 15-minute IV infusion. Subjects will receive 9 doses of LT3001 on Days 5 to

7 (TID q3h). Each subject will be admitted into the study site on Day -1, stay until Day 8, and will have a follow-up visit on Day 14.

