f. Vital signs will include body temperature, blood pressure, respiratory rate, and heart rate. Measurements will be made after the subject has rested in a supine position for at least 3 minutes. Blood pressure will be assessed in seated and supine position at pre-dose and 60 minutes after dosing/infusion, only supine position at 20 minutes after dosing/infusion. Vital signs will be assessed at screening visit, Day 1 to 4 (pre-dose), Day 5 to Day 7 (each LT3001 dosing period at pre-dose, 20 minutes and 60 minutes after infusion is initiated) and follow-up visit on Day 14.

g. A 12-lead ECG assessment will be performed at screening visit and at pre-dose and 1 hour after taking Apixaban on Day 2 to Day 4, and after 1 hour after the infusion is initiated of the first dose of LT3001 on Day 5 or Day 7 and follow-up visit on Day 14.

h. PK blood samples of LT3001 will be collected at pre-dose on Day 5, Day 6 and Day 7 and follow-up visit on Day 14. [REDACTED]

i. PK blood samples of apixaban will be collected at pre-dose on Day 4 and Day 7 and follow-up visit on Day 14. [REDACTED]

j. PK samples of Day 4 and Day 7 will be collected at the second dosing of apixaban on Day 5. [REDACTED]

k. Platelet function test and coagulation test will be measured at pre-dose on Day -1 and at 15 min and 6 hour/15 min after the 2nd dose of apixaban on Day 4.

l. Platelet function test and coagulation test will be measured on the first dose of LT3001 at 15 min after infusion is initiated (end of infusion) on Day 5.

m. Platelet function test and coagulation test will be measured on the last dose of LT3001 at 15 min after infusion is initiated (end of infusion) on Day 7.

n. Coagulation parameters will include PT, INR, aPTT and TT.

o. Hematology tests will include Hb, RBC, MCV, MCH, MCHC, WBC, WBC-DC, and platelets.

p. Clinical chemistry tests will include BUN, creatinine, fasting blood glucose, ALP, ALT, AST, GGT, total bilirubin, total proteins, albumin/globulin ratio, Na, K, Cl, Ca, bicarbonate, uric acid, CK, cholesterol, triglycerides, free iron, and ferritin.

q. Urinalysis will include dipstick urinalysis and microscopic examination.

r. When urine drug/cotinine/alcohol tests and/or clinical laboratory tests including coagulation, hematology and clinical chemistry are performed on Day -4 to Day -2, these tests need not be repeated on Day -1.

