-  The first dose of dabigatran on Day 5, Day 6 and Day 7 will be followed immediately by 0.025 mg/kg LT3001 administered as a 15-minute IV infusion.
-  Physical examination will be performed at screening visit, pre-dose on Day 1, the end of dabigatran single treatment on Day 4, the end of combination treatment on Day 7 and follow-up visit on Day 14.
-  Vital signs will include body temperature, blood pressure, respiratory rate, and heart rate. Measurements will be made after the subject has rested in a supine position for at least 3 minutes. Blood pressure will be assessed in seated and supine position at pre-dose and 60 minutes after dosing/infusion, only supine position at 20 minutes after dosing/infusion. Vital signs will be assessed at screening visit, Day 1 to 4 (pre-dose), Day 5 to Day 7 (each LT3001 dosing period at pre-dose, 20 minutes and 60 minutes after infusion initiated) and follow-up visit on Day 14.
-  A 12-lead ECG assessment will be performed at screening visit and at pre-dose and 1 hour after taking dabigatran on Day 2 to Day 4, and after 1 hour after the infusion is initiated from the first dose of LT3001 on Day 5 to Day 7 and follow-up visit on Day 14.
-  PK blood samples of LT3001 will be collected at 15 min and 45±1, and 60±5 minutes after infusion is initiated.
-  PK blood samples of LT3001 will be collected at 15 min after infusion is initiated (end of infusion).
-  PK blood samples of dabigatran will be collected at 15 min after infusion is initiated (The 24-hour PK samples of Day 4 and Day 7 will be collected prior to the second dosing of dabigatran).
-  Platelet function test and coagulation test will be measured at pre-dose on Day -1 and at 15 min and 6 hours/15 min after the 2nd dose of dabigatran on Day 4.
-  Platelet function test and coagulation test will be measured on the first dose of LT3001 at 15 min after infusion is initiated (end of infusion) on Day 5.
-  Platelet function test and coagulation test will be measured on the last dose of LT3001 at 15 min after infusion is initiated (end of infusion) on Day 7.
-  Coagulation parameters will include PT, INR, aPTT and TT.
-  Hematology tests will include Hb, RBC, MCV, Hct, MCH, WBC, WBC-DC, and platelets.

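### The text of both documents gives apixaban and dabigatran twice daily through Day 7, but the complete Cohort 3 and 4 schedule headers have no Day 7 evening slot; any effect on the Day 7 versus Day 4 comparison is conditional

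*Protocol*

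**What the plan says.** **Dosing text.** Protocol 5.1 gives Cohort 3 "5 mg apixaban twice daily (BID) every 12 hours (q12h) on Days 2 through 7" and Cohort 4 "110 mg dabigatran BID (q12h) on Days 2 through 7". The protocol synopsis and SAP Section 4 state the same regimens.

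**Schedules.** In protocol Table 4 (Cohort 3) the hour header ends "121 124 127 133 145 148 151 169", and the SAP 4.2 Cohort 4 header ends with the same run. Both also contain Hour 109. The header of protocol Table 5 (Cohort 4), as it survives in the public copy, stops at "121 124 127 133 145 148 151".

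**Footnotes.** Footnote d of Table 4 reads "The first dose of apixaban on Day 5, Day 6 and Day 7 will be followed immediately by" LT3001, and footnote d of Table 5 reads "The first dose of dabigatran on Day 5, Day 6 and Day 7 will be followed immediately by" LT3001. Two damaged SAP 4.2 footnotes on partner-drug PK samples read "PK samples of Day 4 and Day 7 will be collected at the second dosing of apixaban on Day 5" (Cohort 3) and "The 24-hour PK samples of Day 4 and Day 7 will be collected prior to the second dosing of dabigatran" (Cohort 4).

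**Analysis.** SAP 8.3 assesses the effect of LT3001 on apixaban and on dabigatran by comparing Day 4 (alone) with Day 7 (with LT3001) on AUC(0-t) and Cmax. It defines AUC(0-t) as running to the last quantifiable concentration. It also derives AUC0-tau for the partner drugs but does not name it in this comparison. Protocol 10.3.2 does list AUC0-tau among the parameters compared.

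**The concern.** The text and the schedules differ on whether an anticoagulant dose is given on the evening of Day 7. Evening slots for the partner drug alone exist on Day 5 (Hour 109) and Day 6 (Hour 133), so the schedules do list such doses; only the Day 7 one is missing. Protocol 7.3 allows no change to the dosing schedule and Section 9 requires adherence to the schedule of activities, but neither says which source governs if they differ.

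Day 7 is also the test day for the effect of LT3001 on each anticoagulant, and partner-drug PK is a primary Part B endpoint. AUC(0-t) has no fixed 12-hour limit. If the evening dose were left out and sampling ran beyond 12 hours, the Day 4 profile would contain two doses and the Day 7 profile one. The missing dose could then look like a fall in exposure caused by LT3001.

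**Working it through.** **1. The plan's own figures.** Protocol 5.1 says three days of dosing reach 97% of steady state for apixaban (half-life 9 to 14 h) and 94% for dabigatran (12 to 17 h). Using 1 − 2^(−72/half-life) at the longest half-life:
- apixaban: 72/14 = 5.14 half-lives, 97.2%;
- dabigatran: 72/17 = 4.24 half-lives, 94.7% (exactly 4 half-lives gives 93.75%).

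Both statements reproduce.

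**2. Dose times.** Twice daily for 6 days is 12 doses, at 25 + 12i for i = 0 to 11: Hours 25, 37, 49, 61, 73, 85, 97, 109, 121, 133, 145, 157. Against the two complete headers, the only dose time without a column is 157.

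**3. Dose rows (supporting evidence only).** By cell position, the Table 4 apixaban row has 10 marks, at Hours 25, 37, 49, 61, 73, 85, 109, 121, 133 and 145. It also lacks Hour 97, which footnote d requires, so it is incomplete. The other three partner-drug rows show 11 marks in columns that cannot be relied on. No row shows 12. The SAP Cohort 3 header is cut at Hour 148 and is not used.

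**4. What a skipped Hour 157 dose would do.** The inputs are the protocol half-lives. The assumptions are one-compartment kinetics with first-order absorption at ka = 0.5 or 1.5 per hour, no interaction, and profiles starting at the morning doses (Hour 73 on Day 4, Hour 145 on Day 7). With k = ln 2/half-life,

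C(t) = Σ ka/(ka − k) × [exp(−k·u) − exp(−ka·u)],

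where u is the time since each dose already given. Dose, volume and bioavailability cancel in the ratio. The Day 7/Day 4 AUC ratios, as ranges over half-life and ka, are:

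| Sampling to | Apixaban, 12 doses | Apixaban, Hour 157 skipped | Dabigatran, 12 doses | Dabigatran, Hour 157 skipped |
|---|---|---|---|---|
| 12 h | 1.010-1.059 | 1.010-1.059 | 1.033-1.099 | 1.033-1.099 |
| 16 h | 1.009-1.053 | 0.847-0.971 | 1.029-1.090 | 0.899-1.019 |
| 24 h | 1.007-1.045 | 0.714-0.842 | 1.025-1.078 | 0.779-0.898 |

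The excess over 1 at 12 h arises because the Day 4 profile starts only 48 h after the first dose, before steady state is complete in the model. Skipping the Hour 157 dose changes the Cmax ratio by at most 0.002.

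**5. What the documents say about the sampling window.** The partner-drug sampling times are redacted or garbled. The Cohort 4 SAP footnote points both ways: it speaks of 24-hour samples, but places them before the second dosing. If that means the evening dose, sampling ends at about 12 h and the first row of the table applies. The Hour 169 column is 24 h after the Hour 145 dose, but it falls on Day 8, when subjects leave the site, so it does not settle the matter.

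**The case against.** The strongest reply is that this is a clerical gap with no demonstrated consequence. Much of that stands.

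- **The regimen is clear in words.** The text is uniform in both documents, and footnote d refers to a first dose on Day 7, which implies a second. A reader might infer that a site cannot follow both text and schedule. The documents do not support that: an absent column does not prohibit a dose, and the adherence sentence in protocol Section 9 covers the study design requirements generally, so it also covers the Section 5.1 regimen. Subjects stay on site until Day 8, so the dose is practicable. The Part B dosing cells of Table 6 are blank and Figures 4 and 5 are not shown in the public copy; they may show the dose.
- **Bias needs two unverified conditions:** the dose is skipped, and sampling goes past 12 h. Neither can be established.
- **Some protection exists.** AUC0-tau is derived and summarised, and dosing records are reviewed when deciding exclusions from the PK analysis set, so a skipped dose should be visible.
- **The decision impact is limited.** The SAP states that no hypothesis testing is done. SAP 8.3 writes the 50-200% and 80-125% criteria in the paragraphs on LT3001 exposure; the partner-drug paragraphs refer only to a similar model. Protocol 10.3.2 applies the criteria more broadly, but every modelled ratio lies inside 50-200%.

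The reply does not remove the conflict itself, nor the fact that the SAP, which states that its methods supersede the protocol's, names an open-ended AUC for the comparison and leaves out the 12-hour one that the protocol lists.

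**Conclusion.** The Day 7 evening dose of apixaban and dabigatran is inconsistently specified: 12 doses in the text, and no Hour 157 slot in the two complete schedule headers. One dose per subject is in doubt for up to 24 subjects (two cohorts of 12). The uniform text, footnote d and the damaged SAP footnotes all suggest that the slot was left out by oversight.

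A reader might infer that the Day 7 versus Day 4 comparison is biased, or that it is plainly unprotected. The documents do not support either reading. If the dose is given, or if sampling stops by 12 h, the missing column does no harm. Only if the dose is skipped and sampling runs longer would AUC(0-t) fall with no true interaction. At 24 h the ratio would be about 0.71-0.84 for apixaban and 0.78-0.90 for dabigatran, under the one-compartment model and the assumed absorption rates. Most of the apixaban range, and the bottom of the dabigatran range, lies below 0.80, so a reading against 80-125% could change; one against 50-200% would not on the point estimates.

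The Day 7 LT3001 infusions (last at Hour 151) and the Day 7 platelet and coagulation tests come before Hour 157 and are not affected.

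**What to change.** 1. Add the Hour 157 (Day 7 evening) slot and dose mark to protocol Tables 4 and 5 and to the SAP 4.2 Cohort 3 and 4 schedules, so that they match the text.
2. In SAP 8.3, make AUC0-tau over the 12-hour dosing interval the compared partner-drug exposure measure on Days 4 and 7 for apixaban and dabigatran, in place of or alongside AUC(0-t). Protocol 10.3.2 already lists it, the SAP already derives it, and it does not depend on the Hour 157 dose.

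The cost is one column in four schedules and one named parameter in two subsections of SAP 8.3. It needs no extra subjects, visits or samples.
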